5.3 Subject Withdrawal Criteria

5.3.1 Screen Failures

Screening evaluations, those performed at pre-selection or screening visit (V0) will be used to determine the eligibility of each subject for enrollment. Subjects who fail to meet eligibility criteria during screening evaluations will be considered screen failures and will not participate in the study.

5.3.2 Removal of Subjects

Subjects may withdraw or be withdrawn from the study for the following reasons:

1. At their own request or at the request of their legally acceptable representative.
2. If, in the site's principal investigator's opinion, after consulting to the Medical Advisor, continuation in the study would be detrimental to the subject's well-being.
3. At the specific request of the sponsor if, in the Medical Advisor's opinion, continuation in the study could be detrimental to the subject's well-being or in case that the subject have incurred in a major violation of the protocol.

4. In case of AEs related to the IMP, particularly allergic reactions or micro- or macro-hemorrhages detected by MRI in the safety control visits (see sections 8.2.6 and 8.3.10).

Subjects who withdraw after being randomized will remain in the study database and their data until the date of discontinuation will be analyzed.

In all cases, the reason for withdrawal must be recorded in the eCRF and in the subject's records.

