6.2.3 Restricted Concomitant Medications during the Study

This section describes medications that are restricted but not prohibited during the study participation:

- Sedatives will not be permitted the night before the neuropsychological tests, particularly neuroleptics.
- Avoid administration of the influenza vaccine or any other vaccination during the 1 month prior and 15 days after each vaccination or until next Safety visit, whatever occurs earlier.
- If a patient with MCI needs to start a dementia treatment or a patient with AD needs modification of their dementia treatment before Int-6m visit (or V16B) or between Int-6m and V21visits (or between V16B and V21B), the investigator should discuss with him/her the benefit/risk balance in order to evaluate if the change can wait until after the Int-6m (or V16B) or V21 visit (or V21B), respectively. If the modification needs to be done before Int-6m (or V16B) visit or between Int-6m and V21 visit (or between V16B and V22B), respectively, the subject must be discontinued from the study treatment, but not from the study follow-up (see Section 5.3.4).
- Treatment with benzodiazepines and nootropics is authorized only at regular and stable doses in steady state (chronic use). Any dose change or treatment modification during the study will be reported both as an Adverse Event and as a change in the Concomitant medication section of the eCRF. If a patient needs to modify the dose before Int-6m (or V16B) visit or between Int-6m and V21 visits (or between V16B and V22B), the decision for the patient to continue with the study treatment will depend on clinical judgment and will be assessed on a case-by-case basis by the Medical Advisor.

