3.1 Analysis Sets

3.1.1 Intent-to-Treat (ITT) Analysis Set

The ITT Analysis Set will include all randomized patients who received any study treatment.

Analysis of all secondary efficacy endpoints will be carried out using the ITT Analysis Set. Patients will be analyzed according to their randomized treatment assignment, regardless of the treatment received.

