3.1.3 Per Protocol (PP) Analysis Set

The Part A PP Analysis Set will comprise of all patients in the ITT Analysis Set who received all doses of study medication (on V1, V4, V7, V10, V13 and V18 in Part A), have attended the safety visit after booster (V20 in Part A), and have no major protocol deviations that could affect the efficacy analyses.

Analysis of the primary efficacy endpoint and secondary efficacy endpoints relating to the characterization of immune response and the assessment of disease biomarkers in Part A will be repeated using the Part A PP Analysis Set.

The Part B PP Analysis Set will comprise of all patients in the ITT Analysis Set who received all doses of study medication (on V1B, V4B, V7B, V10B, V13B and V18B in Part B), have attended the safety visit after booster (V20B in Part B), and have no major protocol deviations that could affect the summary of efficacy.

During the blind review meeting, decisions will be made regarding the PP Analysis Set in terms of whether deviations in Part A affect Part B for inclusion in analysis set.

Summaries of the primary efficacy endpoint and secondary efficacy endpoints relating to the characterization of immune response and the assessment of disease biomarkers over the entire duration of the study (Parts A and B combined), will be repeated using patients who are in Part A PP Analysis Set and the Part B PP Analysis Set.

Patients will be analyzed according to their randomized treatment assignment, regardless of the treatment received.

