3.1.4 Per Protocol Cognition (PPc) Analysis Set

The Part A PPc Analysis Set will comprise of all patients in the ITT Analysis Set who received all doses of study medication (on V1, V4, V7, V10, V13 and V18 in Part A), have attended the safety visit after booster (V20 in Part A), have no major protocol deviations that could affect the efficacy analyses or major protocol deviations that have been classified as “Use of disallowed concomitant medication”, relating to use of Anti-Alzheimer Disease medication.

Analysis of secondary efficacy endpoints relating to the assessment of cognition and quality of life in Part A will be repeated using the Part A PPc Analysis Set.

The Part B PPc Analysis Set will comprise of all patients in the ITT Analysis Set who received all doses of study medication (on V1B, V4B, V7B, V10B, V13B and V18B in Part B), have attended the safety visit after booster (V20B in Part B), have no major protocol deviations that could affect the efficacy analyses or major protocol deviations that have been classified as “Use of disallowed concomitant medication”, relating to use of Anti-Alzheimer Disease medication.

During the blind review meeting, decisions will be made regarding the PPc Analysis Set in terms of whether deviations in Part A affect Part B for inclusion in analysis set.

Analysis of secondary efficacy endpoints relating to the assessment of cognition and quality of life over the entire duration of the study (Parts A and B combined), will be repeated using patients who are in Part A PP/PPc Analysis Set and the Part B PP/PPc Analysis Set. (See Section [3.1.3](#))

Patients will be analyzed according to their randomized treatment assignment, regardless of the treatment received.

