6.1.3 Analysis of Secondary Outcome Variables

No adjustments will be made for multiple testing of study parameters. Therefore, interpretation of p-values for the analyses of secondary outcomes should be considered descriptive in nature.

The following analyses will be performed for all secondary outcomes specified in section 4.2.2 of this SAP (above), using the ITT Analysis Set:

1. The MMRM analysis described in section 6.2 will be repeated for all continuous parameters.

With the exception of levels of anti-A β 40 antibodies in CSF and plasma, the dependent variable will be the change from baseline in secondary outcome as the dependent variable; treatment, protocol-specified visits, treatment-by-visit interaction, and amyloid positivity as the fixed effects; baseline secondary outcome and baseline age as covariates; and measures within-patient at each visit as a repeated measure.

For the analysis of levels of anti-A β 40 antibodies in CSF and plasma, the dependent variable with the be recorded outcome value (i.e. not the change from baseline) and the baseline outcome covariate will be removed from the model.

The following factors may also be included in the model: ApoE carrier status, baseline use of AD symptomatic medication and clinical subgroup – MCI or vmAD, if found to be significantly associated with the response measure ($p < 0.15$).

2. A plot of LS mean change over time will be presented by treatment group.

All analysis will be repeated for baseline a-PET positive and baseline a-PET negative patients separately for the following parameters:

1. Disease biomarkers – all parameters listed in section 4.2.2.2 above.
2. Cognition assessment – MMSE, CDR-SB, RBANS, ADCS-ADL MCI, C-SSRS, IGE, EQ-5D-5L and TMT.

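### Protocol 5.3.2 item 3 lets the sponsor end a patient's study follow-up, not only treatment, for an undefined major protocol violation

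*Protocol*

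**What the plan says.** The list in Protocol 5.3.2 sits under one permissive lead-in, which speaks of leaving the study rather than stopping treatment. Item 3 gives the sponsor two alternative grounds. The first is detriment to well-being in the Medical Advisor's opinion. The second stands alone: "or in case that the subject have incurred in a major violation of the protocol". For randomised subjects who withdraw, "their data until the date of discontinuation will be analyzed".

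Item 4, under the same lead-in, reads "In case of AEs related to the IMP, particularly allergic reactions or micro- or macro-hemorrhages detected by MRI in the safety control visits" and refers the reader to 8.2.6 and 8.3.10.

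Other sections separate treatment from follow-up:

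- **Protocol 6.2.3.** When dementia treatment has to change before the V16 or V21 assessments, "the subject must be discontinued from the study treatment, but not from the study follow-up".
- **Protocol 4.9.3 and 5.3.4.** Patients who stop treatment early are asked to attend the remaining safety visits, through V25 in Part A.
- **SAP 3.1.3 and 3.1.4.** Major deviations are an analysis-set matter. Patients in the PP set must "have no major protocol deviations that could affect the efficacy analyses". The PPc set adds deviations for disallowed medication "relating to use of Anti-Alzheimer Disease medication".
- **SAP 3.1.1.** Secondary efficacy uses the ITT set: "Patients will be analyzed according to their randomized treatment assignment, regardless of the treatment received".

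**The concern.** An analysis by randomised arm, whatever treatment was received, needs data collected after treatment stops. A rule that ends participation because of a protocol violation removes those data at the sponsor's choice. The SAP already has a way to set such patients aside in sensitivity analyses without losing their observations. Well-being is covered by item 2 and by the first half of item 3. For a patient who consents and is not at risk, the violation ground therefore adds little beyond the power to end follow-up.

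Two kinds of data are at stake. One is the later cognition, MRI, amyloid-PET and CSF assessments that feed the secondary models. The other is new non-serious adverse events, because Protocol 8.2.1 records events only to the last day of participation.

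**Working it through.** No figure in the plan is alleged to be wrong. The check is a comparison of texts, an illustrative visit count and a check on primary power.

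**1. Texts side by side**

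| Situation | Treatment | Follow-up |
|---|---|---|
| Major violation, 5.3.2 item 3 | ends | may end; data used only to discontinuation |
| Dementia-drug change, 6.2.3 | must stop | must continue |
| Early treatment stop, 4.9.3 and 5.3.4 | stopped | remaining safety visits requested |
| Major deviation, SAP 3.1.3 and 3.1.4 | not addressed | not addressed; excluded from PP or PPc only |

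Only 6.2.3 is a direct contrast. 4.9.3 and 5.3.4 also foresee complete withdrawal.

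**2. What one withdrawal can cost.** Take a patient removed after V16 (week 24) and before V17 (week 40). Later Part A visits are V17 (week 40), V20 (44), V21 (50), V23 (77) and, for some patients, V25 (104).

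| Assessment | Follow-up kept, Part A ends at V23 | Follow-up kept, Part A ends at V25 | Withdrawn from study |
|---|---|---|---|
| Face-to-face visits | V17, V20, V21, V23 = 4 | 5 | 1 |
| Cognition | V21, V23 = 2 | 3 | 1 |
| MRI | V17, V21 = 2 | 3 | 1 |
| Amyloid-PET and CSF | V21 = 1 | 2 | 1 |

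The last column is the premature discontinuation visit, which carries the V21 assessments (4.9.3). The middle columns are upper bounds. They assume full attendance at visits that are only requested, and full assessments at what 5.3.4 calls minimum safety visits. When Part A ends at V23, the PET and CSF count does not fall; only its timing changes.

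The discontinuation visit does not clearly fill the gap. 5.3.4 places it within 15 days of the last dose. In this example that dose was V13 (day 112), and 112 + 15 = day 127, before V16 at day 168. The visit therefore falls at an unscheduled time. The secondary MMRM has "treatment, protocol-specified visits, treatment-by-visit interaction, and amyloid positivity as the fixed effects", and the SAP gives no rule for placing a discontinuation visit among them. That gap affects every dropout; 5.3.2 only adds to it.

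**3. Primary power.** Inputs from Protocol 9.2: difference 1.778 OD, SDs 2.0 and 1.0, one-sided alpha 0.025.

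Power = Φ(1.778 / √((2.0² + 1.0²)/n) − 1.96), with n per arm.

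- n = 15, the stated minimum: 1.778/0.577 − 1.96 = 1.12, giving 86.9%. Noncentral-t versions give 84.4% (pooled) and 83.5% (Welch). The protocol's 85% with 15 per arm is reproduced on the normal approximation.
- n = 35, the expected completers: 1.778/0.378 − 1.96 = 2.74, giving 99.7%. The stated figure of more than 85% holds.
- Assumed further losses of 5%, 10% and 15% leave 33, 32 and 30 per arm, giving 99.5%, 99.4% and 99.2%.

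These loss rates are assumptions; the documents give none. For context, the plan already expects 120 − 70 = 50 patients (42%, stated as about 40%) not to complete.

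**The case against.** The case for leaving the text alone has real substance.

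- **The power is discretionary.** 5.3.2 permits withdrawal and does not require it. That stands, but the discretion comes without criteria.
- **The protocol is not uniformly against study withdrawal.** 4.9.3 covers complete discontinuation for any reason, and 5.3.4 covers leaving the trial because of an adverse event. A reader might infer that 5.3.2 contradicts all three sections; the documents support that only for 6.2.3.
- **A clash in one patient is not shown.** A reader might infer that item 3 overrides 6.2.3 when dementia medication changes, because the PPc definition counts some anti-Alzheimer use as a major deviation. But 6.2.3 is specific and mandatory, and it describes those medicines as restricted, not prohibited. SAP 3.4 classes deviations at data review meetings before database lock, for analysis sets, not for removing patients. The clash arises only if the sponsor treats such a change as a major violation.
- **Item 4 is weaker.** A reader might infer that patients with ARIA leave the study. Item 4 points to 8.3.10, where every specified stopping action concerns treatment and follow-up scans are requested at 2, 4, 6 and 12 months. Treatment-only withdrawal was probably meant.
- **Some safety follow-up survives.** Adverse events that led to leaving the trial are followed to resolution (5.3.4), and SAEs to resolution or stabilisation (8.3.9). SAEs more than 14 months after the last dose are still reportable if the investigator considers them related. New serious events are therefore not simply lost; the clear loss is new non-serious events and scheduled visits.
- **Some violations may justify leaving**, such as invalid consent. This is right, and the fix needs an exception for it.

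**Conclusion.** The point holds for item 3. An undefined violation, with no safety condition, can end the follow-up of a randomised and dosed patient, while the SAP needs that follow-up and already handles deviations another way. The result would be avoidable missing data in secondary outcomes and an end to new non-serious adverse-event collection for the patients concerned.

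The size is limited. The outcomes affected are exploratory, and SAP 6.1.3 calls their p-values descriptive. Frequency of use and dependence on arm cannot be computed from the documents. A reader might infer bias in the primary results; this is not supported. Primary power stays above 99% under the assumed losses, and nothing in the documents shows that the immunogenicity or safety conclusion would change. This is a cheap improvement, not a flaw in the primary analysis. Item 4 is an optional wording alignment only.

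**What to change.** In 5.3.2 item 3, make a major protocol violation at most a ground for stopping study treatment. Follow-up then continues under 5.3.4, and the analysis is handled through the PP and PPc sets. Except cases where consent is withdrawn or invalid, or where continued study procedures would harm the patient.

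Optionally, reword item 4 so that adverse events related to the product lead to suspending or stopping treatment where indicated, as 8.3.10.1 already sets out for ARIA. Which events stop treatment remains a clinical decision.

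The cost is protocol wording, plus a few already planned visits for patients who would otherwise have left. The analysis sets already exist.

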5.3.3 Subject Replacement

It is expected that 120 patients (60 in verum and 60 in placebo) with a-MCI or vm-AD will be included in the clinical trial as per protocol, from whom ~ 40% will prematurely withdraw. However, since all enrolled patients who receive any amount of study drug will be valid for the primary safety analysis and the number of patients expected to complete the clinical trial taking into account a 40% of premature discontinuations (approximately 70) will have more than 85% power to evaluate the primary efficacy endpoint, there will be no need to replace withdrawn patients who have received at least one dose of the IMP or placebo, as correspond. Therefore, patients who have been randomized and did not receive any dose of IMP or placebo will be replaced.

5.3.4 Follow-up of Subjects Withdrawn from Study Treatment

Subjects who receive any amount of investigational product and discontinue early from the study treatment will be requested to continue with the remaining safety assessment visits (without any more treatment administration nor related phone interviews). The following visits are those considered minimum “safety assessment visits” to be performed in subjects withdrawn from study treatment (as applicable according to the time of withdrawal):

- Safety control visits
 - Face-to-face visits: V3, V6, V9, V12, V15, V16 (Int-6m), V17, V20, V21, V23 and V25 (Final visit) [Part A]; V3B, V6B, V9B, V12B, V15B, V16B, V17B, V20B, V21B and V22B [Part B]

There is no need to perform any additional Vaccination Visit nor phone interviews.

Withdrawn subjects should receive at least a premature discontinuation visit within the 15 days after their last treatment's administration (PDV; see section 4.9.3). If a randomized subject withdraws the study before receiving the first IMP administration, the following assessments of the PDV will not be needed: electrocardiogram; urine analysis (test strip); hemogram, biochemistry, biological activity, MRI, a-PET, CSF.

In accordance with good clinical practice (GCP), patients that discontinue the trial prematurely due to adverse events will be followed-up until resolution of the AE, properly documenting both the cause of premature withdrawal as well as management of data collected and the subsequent treatment received by the patients.

[figure not shown]
6 TREATMENT OF SUBJECTS

See Section 4.4 for the treatment(s) to be administered, including the name(s) of all the product(s), the dose(s), the dosing schedule(s), the route/mode(s) of administration.

6.1 Administration and Timing of Investigational Products for Each Subject

Treatment will consist of the administration of six 1 mL doses of verum (the IMP; ABvac40 vaccine) or placebo (comparator; the vaccine vehicle without the API) along a “treatment period” spanning for 42 weeks (10 months) for both Part A and Part B (see Figure 1). The first five doses will be administered at four-week intervals on visits V1, V4, V7, V10 and V13 [Part A] and V1B, V4B, V7B, V10B and V13B [Part B]. The sixth dose, a delayed booster shot, will be administered at V18 [Part A] or V18B [Part B], 26 weeks after the fifth dose.

Figure 1 Treatment administration schedule scheme

ABvac40 dose (or placebo) is dispensed in 1 mL vials, ready for direct injection. Each patient will be assigned a treatment kit (blister) containing 8 vials (verum or placebo as corresponds) including 2 spare vial. For Part B treatment kits will contain 6 vials of verum or placebo.

All treatments will take place at the trial center and will be administer by trained staff from each site.

Injections will be administered subcutaneously (sc) proceeding with special care to avoid intravenous administration, gently aspirating with the syringe before injecting. As a first option the lateral aspect of the arm will be used, about 8-10 cm above the elbow. As a prerequisite the regional lymph node group must be intact, if neither arm has intact lymphatic drainage, the injection will be administered to an anterior thigh, roughly half way between the groin and knee.

After each treatment the patient will remain under observation for 2 hours in the center. At the end of this time, vital signs will be assessed and a thorough examination carried out including inspection of the injection site to assess any reaction to the vaccine.

6.1.1 COVID-19 Testing

6.1.1.1 Part A

All patients who will attend their V18 after April 2020 must be tested for COVID-19 by PCR method before receiving the study medication (Urgent safety notification has been send to Competent Authorities).

The aforementioned patients must sign a specific ICF authorizing this test. In case they refuse, they will continue participating in the study but they will not receive the study treatment.

After authorization, the required samples will be taken by a trained study staff or delegate and sent to the central laboratory (██████████) where a standard PCR test for COVID-19 detection will be performed.

After 24-48h, the patient will be communicated with the results. In case the patient test negative for COVID-19, he or she will continue with the study procedures (including receiving the study treatment) normally.

In case the patient test positive for COVID-19, the PCR test will be repeated until the patient test negative and is asymptomatic. During this time, the patient will not receive the study treatment. Under any delay scenario, the subsequent visits will be re-scheduled accordingly.

6.1.1.2 Part B

All patients must be tested for COVID-19 during the Part B vaccination visits before receiving their study medication, unless the patient has already overcome the disease (it has to be documented) and remains asymptomatic.

At each vaccination visit, the patients will perform a rapid serological test at the study site to detect SARS-CoV-2 antibodies in serum.

In case the patient test positive and he or she is completely asymptomatic for COVID-19, he will continue with the study normally.

In case the patient test negative, a PCR test for COVID-19 detection will be performed. The required samples will be taken by a trained study staff or delegate and sent to the central laboratory (██████████) where a standard PCR test for COVID-19 detection will be performed.

After 24-48h, the patient will be communicated with the results. In case the patient test negative and remains completely asymptomatic for COVID-19, he or she will continue with the study procedures (including receiving the study treatment) normally.

In case the patient test positive for COVID-19, the PCR test will be repeated until the patient test negative and is asymptomatic. During this time, the patient will not receive the study treatment. The administration of the study treatment can be delayed for up to one month. In case it should be delayed beyond one month, the vaccination will be skipped. Under any delay scenario, the subsequent visits will be re-scheduled accordingly.

